Canada and other nations (43, 44). For each of the 11 Partnership schools (5 in MD, 6 in SC) in the summer of the three intervention vs. comparison years, developers of The Guide Drs. [name] or [name] will conduct a one-day training involving the SBH clinicians and senior trainers (1 from SC and 1 from MD), as well as with three teacher leaders recruited from each of the schools, with one each from 6th, 7th, and 8th grade. For individuals who cannot attend the summer training, the research team will host a compensatory training utilizing video segments recorded during the summer training. Following one-day training, coaching calls and webinars will be conducted with this group by [name] or [name] (alternating involvement with each site). The SBH clinicians and these teachers will be active on the schools' MTSS teams, and will in turn provide training on The Guide to these teams, and clinicians will use materials in sessions with students and families. In each school, this group will also use grade-level meetings, MTSS meetings, and other avenues to disseminate information on The Guide to other teachers, and will encourage teachers to sign up and go through a free on-line course on it. The online self-study course takes between 4 to 6 hours to complete, and is associated with continuing education units and teacher education certificates from the University of British Columbia (<http://educ.ubc.ca/>), which we believe will be an important incentive (e.g., facilitating promotion opportunities). Teachers and clinicians involved in implementing The Guide program will complete The Guide Curriculum Assessment, a measure with adequate psychometric properties (43,44) at the beginning and end of each school year. Students receiving Tier 3 intervention will also complete this measure (student version) at intake and every three months, integrated into the Tier 3 measurement strategy (see below). As result of the COVID-19 crisis in late spring of 2020, schools began implementing distance learning for all students. Because of this shift, teachers were temporarily unable to facilitate The Guide curriculum in classrooms as planned. One Maryland school teacher and clinician have continued to facilitate a live, interactive session using the Blackboard platform, in addition to one South Carolina teacher who is using the Google platform. These two schools are able to maintain essential components of the material as articulated by consultants [name] and [name], and seek additional guidance from the study team and consultants as needed. For schools that are unable to facilitate virtual delivery of The Guide curriculum, clinicians will facilitate regular meetings with teachers at their respective schools. These meetings are intended to achieve two goals: 1) review The Guide content to increase knowledge and confidence and 2) create an implementation plan for delivering The Guide in classrooms when schools resume in-person instruction. The study team will track all of these activities via monthly reports submitted by clinicians and teachers, including whether sessions were held virtually or in person. With IRB approval from all sites, class rosters including school-issued student identification numbers will be collected by the study team. This strategy will serve as an additional enrollment strategy, as the team will be able to include variables related to classroom participation with The Guide in later analyses of student data (e.g., grades, attendance, discipline referrals) to assess any changes that may be associated with the curriculum. All decisions related to The Guide curriculum are made through collaboration with [name] and associates at teenmentalhealth.org. In addition, [name] will serve as a content expert on ECHO calls with teachers and clinicians during years 2 and 3 of the study.

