### **Study Design.**

*Measures and Measurement Plan.* All measures chosen for use in the study are in the public domain and have strong psychometric properties (e.g., internal consistency, test-retest reliability, concurrent validity). There will be two streams of data collection involving students. The first will be data collected to reflect school-wide impacts of the Partnership Condition focusing on academic record variables of students' grades, attendance, lateness and discipline referrals (including office discipline referrals and suspensions), and school climate. School-wide academic record data will be collected for all students and de-identified to the research team (it is considerably less burdensome for schools to share deidentified data for all students than to share for a sample of them). School climate data will be collected for a sample of about 60 students (3 randomly selected classrooms), and 25-40 staff (requesting all staff complete) at each of the 22 schools. School-wide academic record data will be collected once annually for the academic year prior to study start (2018-19), and will be collected each year for the three years of intervention vs. comparison, per procedures that we are replicating based on the current NIJ-funded RCT. Selected students and staff will complete the School Climate Survey (SCS) a free, online school climate survey from the US Department of Education (<https://safesupportivelearning.ed.gov/edscls>). The SCS is available as a web-based platform and includes a suite of school climate surveys for students, instructional staff, and non-instructional staff. Staff and students will be asked to

PRINCIPAL INVESTIGATOR: [name]

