*Aim 2: Evaluate the impact of the Partnership enhancements on students' social, emotional/behavioral (EB), and academic outcomes.* For this primary aim, there will be two sub-aims: Aim 2a will evaluate the impact of the Partnership enhancements on school-wide academic record variables of grades, attendance, lateness and discipline referrals. Aim 2b will focus on students receiving Tier 3 services and will assess their social and emotional/behavioral (EB) functioning. To assess social functioning, the Child and Adolescent Social and Adaptive Functioning Scale (51) will be completed by students. The CASAFS includes 24 items measuring students' functioning in four key social roles: school performance, peer relations, family relations, and home duties/self-care. Additionally, both "internalizing" EB problems, which include problems of depression, anxiety and exposure to trauma, and "externalizing" EB problems, which include conduct and attention problems, will be measured for students receiving Tier 3 services. Student EB functioning will be measured by parent and student report forms of the Brief Problem Checklist (52), a 12-item questionnaire that measures externalizing and internalizing problems. Derived from the comprehensive Child Behavior Checklist (53), it is designed for repeated periodic assessment of clinical progress, yielding both an internalizing and externalizing subscale (52). Please note that academic variables collected above school-wide for stream 1 data collection, will also be used for stream 2 data collection for students receiving Tier 3 services. Changes in the above variables will be assessed for students for the academic quarter before receiving mental health services and the academic quarter after services have been completed.

*Additional Measures.* In addition to measures directly reflecting study aims, secondary aims will be addressed by measures reflecting the potential impact of the two Partnership enhancements will be collected at the same time intervals for students receiving Tier 3 services. For the enhancement focused on mental health education and stigma reduction, students will complete The Guide Curriculum Assessment (GCA) reviewed previously (43,44). The GCA includes subscales assessing Mental Health Literacy in three dimensions: Mental Health Knowledge (MHK; 28 items),

PRINCIPAL INVESTIGATOR: [name]

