**Analytic Plan.** The proposed project is a cluster-randomized controlled trial (J=22 schools; 11 per treatment arm) comparing the efficacy of Wellness vs. Partnership services. As a general analytic plan, we will use hierarchical linear modeling (HLM) to evaluate the project aims. Specifically, we will use two-level HLM models to account for students being nested within schools. Though one might conceptualize this proposal as a three-level model (i.e., students nested within schools, and schools nested within sites), it would be neither feasible nor recommended to model site as a multilevel variable given there are only two sites in the design (56). In line with best practice, we will integrate site (i.e., SC vs. MD) as a covariate in the statistical models to contain any potential effects of this variable. Based on prior research conducted by the team, we expect intraclass correlations (ICCs) to warrant the incorporation of random intercepts to account for violations of independence. We will also test independence assumptions for the treatment parameters to determine how sensitive treatment effects are to potential violations of independence, and will include random slopes to account for nested treatment effects if ICCs exceed .01. For transparency, we will report both fixed and random effects (i.e. intercepts and slopes) of the model. Additionally, we will iteratively subset the model using a k-1 sensitivity analysis to determine the influence of individual sites on parameter estimates. We will estimate statistical models using full information maximum likelihood to accommodate any missing data (57). We will use maximum likelihood with robust standard errors to estimate models that include the Zero Inflated Poisson link function for count

PRINCIPAL INVESTIGATOR: [name]

outcomes (e.g. absences, referrals). This general analytic framework will be used in aims 1 and 2. Details, exceptions, and modifications to it are discussed below.

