The second avenue of recruitment will be for students receiving Tier 3 treatment services. These students/parents will be consented using electronic consent (e-consent) in REDCap, with the consent form appended at the beginning of the survey. Participants and their parents will be required to go through the informed consent process and digitally sign the consent form using a mobile tablet device before proceeding into the survey questionnaire. MUSC has successfully piloted e-consent in REDCap with other IRB approved research studies. Given challenges with parents' ability to attend meetings at the school to complete the enrollment process, the study team developed protocol to allow for consent to be gained via phone and intake to be completed remotely via phone or computer. This flexibility allows enrollment to continue, and not be hampered by potential transportation or financial constraints that may otherwise prevent low-income families from participating. Additionally, as result of the COVID-19 crisis, procedures were developed to allow students to assent into the study via telephone or video conference. Students and parents may provide assent/consent via phone, after viewing consent materials and having the opportunity to ask questions of the clinician. Intake assessments can be completed verbally (via phone or video conference) or a link to complete surveys online may be sent via email or directly through the REDCap program by the clinician or research manager.

PRINCIPAL INVESTIGATOR: [name]

Based on current prevalence data, twenty percent (2,14) of students are expected to present with mental health challenges (n= 4,000). Of these students, based on the experience in similar studies the research team estimates that 30% will consent to participate representing the recruitment goal of 1,225 students by the end of the 2022-23 academic year. The rate of recruitment will be higher initially due to enrollment of students currently receiving services, however, over the course of the study an average of 35 students per month (during the academic year only, or four years times 9 months for 36 months total) will be enrolled. Note: significant changes to enrollment targets have been made during this project largely related to the unanticipated and unprecedented impact of the COVID-19 pandemic which temporarily closed school buildings and changed mental health care services starting in March 2020.

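### The academic-record outcomes span in-person, closed and remote schooling with no adjustment for mode, so the Tier 3 before-after change mixes behaviour with recording mode, in either direction

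*Combined protocol and SAP*

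**What the plan says.** Under Aim 2 in Study Design, "Aim 2a will evaluate the impact of the Partnership enhancements on school-wide academic record variables of grades, attendance, lateness and discipline referrals". The Measures and Measurement Plan spells out the record variables as "attendance, lateness and discipline referrals (including office discipline referrals and suspensions". It sets the timing: "School-wide academic record data will be collected once annually for the academic year prior to study start (2018-19"), after which they "will be collected each year for the three years of intervention vs. comparison". Elsewhere the same section counts four intervention years, 2019-20 to 2022-23.

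The record variables are reused for Tier 3 students, where change is taken between "the academic quarter before receiving mental health services and the academic quarter after services have been completed". The Tier 3 model modifications add rolling entry and difference scores.

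On the pandemic, the Partnership intervention section says that "schools began implementing distance learning for all students", and the Recruitment Plan refers to the "COVID-19 pandemic which temporarily closed school buildings and changed mental health care services starting in March 2020". The Analytic Plan notes that The Guide was delivered virtually in some phases and later in classrooms.

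For analysis, the Analytic Plan specifies two-level models with site as a covariate, and "models that include the Zero Inflated Poisson link function for count" outcomes such as absences and referrals. It mentions no exposure offset, school-year term or mode term.

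**The concern.** An office referral, a suspension or a late arrival largely presupposes a student in a building. Attendance can be taken online, but not necessarily by the same rule. The plan adapts school climate, telehealth sessions, The Guide and consent to the pandemic. For the record variables it gives no remote definition, no count of in-person days, no period term and no sensitivity analysis by mode.

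A Tier 3 student seen in person before services and remotely afterwards shows fewer referrals with no change in behaviour. The reverse pair shows more. Full-information likelihood does not help, because an event that could not be recorded enters as an observed zero, not as a missing value. A site main effect does not absorb disruption that varies by period within a state.

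At stake are the precision of the Tier 3 academic results, how their mean changes are read and, if service timing differs by arm, the arm contrast. Without a rule, the choice of periods also stays open until the data have been seen.

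**Working it through.** The documents give no figure for this issue, so there is none to reproduce. The calculation below is an illustration with no treatment effect.

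**Inputs from the documents.** Four intervention years, hence 16 quarters; a 9-month school year; closure from March 2020; the before and after quarter rule; rolling entry; an expectation of longer services in Partnership (Outcomes).

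**Assumptions (not in the documents).**
- Quarter 4 (spring 2020) is closed, and r = 0, 2 or 4 quarters of 2020-21 are remote.
- Starts are uniform over quarters 1 to 15. The before quarter is the one preceding the start; for a start in quarter 1 it lies in 2018-19.
- Duration is 1 + Poisson(mean − 1) quarters, with mean 2 (Wellness) or 3 (Partnership).
- The recorded rate is 1 in person and .1 when closed or remote.
- Only pairs whose after quarter falls within the 16 quarters are counted.

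**Tier 3 pairs.** Let m be the share of pairs in two modes. Mean change is .9 × (share remote to in person − share in person to remote). Enumerating all start and duration combinations gives:

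| r | m, mean 2 | m, mean 3 | Mean change, 2 | Mean change, 3 | Arm difference |
|---|---|---|---|---|---|
| 0 | 13.7% | 12.9% | .005 | .022 | .017 |
| 2 | 36.9% | 40.1% | .007 | .036 | .029 |
| 4 | 41.8% | 54.0% | .007 | .037 | .030 |

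Mismatched pairs go both ways. At r = 4 and mean 3, 24.9% go from in person to remote and 29.0% the other way, so the net change is a small rise: .9 × (.290 − .249) = .037.

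With care of 2 v 2.2 quarters the arm differences are .003, .004 and .004. If four times as many students start in the first quarter (the Recruitment Plan expects faster early enrolment), the 2 v 3 differences become −.003, −.026 and −.033. The sign therefore depends on when students start.

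**Variance.** Take an in-person mean of 1 per quarter and a stable student rate with mean 1 and variance v. In person, the student's level cancels and the change score has variance 1 + 1 = 2. With mixed modes it is

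E(sum of the two mode rates) + .81 × m × (1 + v) − (mean change)².

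For r = 4, mean 3, v = 1: 1.345 + .81 × .540 × 2 − .037² = 2.22, or 11% more. With v = 2: 1.345 + .81 × .540 × 3 − .037² = 2.66, or 33% more. Over the six cells the increase is 2% to 13% for v = 1 and 10% to 33% for v = 2. The shift at the average rate alone, (.81m − mean change²)/2, is 5% to 22%. Roughly 5% to 25% is a fair summary, as an order of magnitude.

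**Aim 2a.** Non-comparable periods are (1 + r)/16 = 6% to 31% of the quarters, or (1 + r)/12 = 8% to 42% if records cover only three years. For 2019-20 alone, losing 2 to 3.5 of 9 months lowers the annual count by 22% to 39%. Between arms, the spurious ratio is (1 − share in Partnership)/(1 − share in Wellness). Equal shares of 30% give 1.00. If nothing is recorded remotely, 40% in Partnership v 30% in Wellness gives .60/.70 = 0.86.

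**The case against.** The strongest reply is that Aim 2 is a concurrent randomized contrast. Schools are allocated by strata within each state, and site is in the model, so a closure shared by both arms cancels. This stands for Aim 2a. A reader might infer that the closure manufactures a Partnership effect there, and the documents do not support that. An absolute difference is diluted by roughly the non-comparable share. A rate ratio, the scale of the count part of the planned model, is not diluted by periods that record nothing in either arm.

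A reader might also infer that counts must fall by construction. They need not: reverse pairs show rises, the uniform-start means above are small net rises, and remote absences could move either way. Nor do the documents say that recording was the same in every mode; they are silent.

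The zero-inflation worry is limited too. Annual extracts mean that spring 2020 shortens a year's count without turning the whole year into a zero, and a difference score can be negative, so it cannot be zero-inflated Poisson.

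Finally, the remote quarters, remote rate and care durations are all assumed. That is true, and it is why the arm bias is stated as conditional. The reply does not reach the Tier 3 rule: under rolling entry, the two quarters of a pair often fall in different modes, and randomization does not fix the timing of the after quarter.

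**Conclusion.** The gap is real and worth correcting. Followed as written, the Tier 3 academic change combines behaviour with recording mode. The firmest result is the share of mismatched pairs, about 13% to 54% under the stated assumptions, with an added variance of roughly 5% to 25% in an illustrative overdispersed count. Arm bias is possible only if timing or mode differs by arm. It is about .02 to .03 of the in-person quarterly rate for 2 v 3 quarters of care with uniform starts and near zero for 2 v 2.2, and its sign can reverse with early-loaded starts. For Aim 2a the consequence is lost information and diluted absolute differences, not a false arm effect.

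**What to change.** Tag each school-year and quarter, by state (by school if modes differed within a district), as in person, closed or remote, and define each count for each mode.

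- **Aim 2a:** add school-year and state-by-year (or mode) terms. Use an in-person-days offset for the count outcomes where days are available. Give a sensitivity analysis limited to in-person school years; annual extracts cannot split 2019-20.
- **Tier 3 academic change:** keep all pairs in the main analysis and adjust for the calendar period and mode of the before and after quarters. Report mismatched pairs by arm. Show same-mode pairs as a sensitivity analysis only, because that restriction selects on when services ended, which treatment may change.

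The cost is a calendar lookup and a few model terms. One drawback remains: the after-quarter mode term conditions on timing that arises after randomization. The plan already does something similar by interacting treatment with weeks of treatment. Results with and without the term should both be shown.

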**D. Study Design/Approach.** The study will involve 22 middle schools (12 in SC, 10 in MD) in a cluster-RCT, with all schools receiving the Wellness intervention and half of the schools (6 in SC, 5 in MD) randomized to receive enhanced intervention including the two SEs (Partnership). Stratified random assignment of schools to the Wellness Group or the Partnership Group will be conducted. We will then use validated procedures (23, 24) to further stratify schools within each state. We will construct a composite inflate-suppress score derived from school data on rurality, average number of students per grade, percent white, percent receiving free/assisted lunch, and average school test performance. Rurality within the two study sites will be operationalized by using a federally developed classification system used by The US Census Bureau (i.e., a 9-point, "Rural-Urban Continuum"). The coding scheme will distinguish three metro county categories based on population size, and six non-metro county categories based on degree of urbanization, as well as adjacency to other areas and metro proximity. Per operationalization of rurality in the federally-based coding continuum, we can confirm that the SC study sites contain county classifications of rural and suburban, while the MD site is exclusively urban. We will separate this composite into three strata and randomly assign schools from these strata to receive either the Wellness Group or the Partnership Group.

In the 5-year longitudinal design, Year 1 will involve administrative start up, collection of pre-assessments and intervention launch; Years 1-4 will involve intervention versus comparison while participants are in 6th through 8th grades. Year 5 will involve analyses and dissemination. A comprehensive implementation manual will guide the study and will be updated and improved regularly through active guidance of a Stakeholder Advisory Board (SAB, see Tables 3 and 4 in Appendix). The SAB will provide significant input as this manual is developed during the study start-up period from January through July, 2019, and progressively improved through study duration (see Gantt chart in Figure 1 of the Appendix for a review of all study activities in time).

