complete the survey, which assesses the dimensions of engagement, safety, and environment once annually at the end of each academic year for the four years of intervention vs. comparison (2019-20, 2020-21, 2021-22, 2022-23). Due to the COVID-19 pandemic, the team was unable to collect SCS data from students in [REDACTED] schools during the first academic year (2019-2020). While this means a compromised set of Year 1 data on school climate for the [REDACTED] site, such measurement is intact for SC, and we will still be able to document trends in time in school climate in [REDACTED] for years 2-4 of the intervention vs. comparison period. Additionally, the study team will collect rosters of classrooms receiving The Guide Curriculum (GC). This will enable two sets of analyses: first, we will document which students receiving Tier 3 services and participating fully in the study are exposed to GC and account for this in terms of interventions received in analyses. Second, this will significantly expand a second level of enrollment for the study, as we will have de-identified academic records for all students (related to recently approved amendments), and will explore impacts of the GC on academic record variables (e.g., discipline problems, grades, attendance) for students in classrooms in Partnership schools receiving it compared to students in demographically comparable classrooms from Wellness schools that do not receive it.

The second stream of data collection will focus on students receiving Tier 3 services and consenting to be in the study. Clinicians will collect these measures with students and families at intake, every three months, and at case closure, using an electronic data portal coordinated by [name] and the Informatics Team at the Medical University of South Carolina (MUSC). The measurement strategy for each of the study aims is presented here:

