In addition to primary intent to treat analyses, we plan to use quasi-experimental methods to test dose-response, and treatment engagement on a core aspect of the Partnership Condition – the mental health literacy intervention through the program, The Guide. In Partnership schools, this intervention has continued to be implemented through all phases of the pandemic, going from virtual in some phases to in-person in classrooms. We are able to access student academic records (demographics, grades, attendance, discipline) for students in Partnership classrooms receiving The Guide, as well as students in comparable wellness classrooms not receiving it. Per below, we have a large sample size to pursue these supplementary analyses. In these analyses, we will be overpowered (MDES below .1) to understand the impact of this mental health literacy intervention on student functioning, including examining dose of intervention given variability in teachers' delivery of it. We also have broader school climate data to explore the impact of the Partnership intervention on this variable (collected fall, 2019; fall, 2020; fall, 2021; spring, 2022; and spring, 2023).

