Please note, we will analyze data related to services received and outcomes for students of varying race/ethnicity as a supplemental, exploratory aim. Because of increased attention to cultural issues, it is possible that the Partnership intervention may have additional benefits in reducing disparities in services and outcomes for youth of color. Should findings indeed point to benefits of the Partnership intervention, these will be integrated into our dissemination plan and help to fuel critically important future research.

**Study Population and Setting.** Intervention will begin during the 2019-20 school year, and it will continue through the 2022-2023 school year. The study sample will include students from 22 middle schools, with 12 schools from SC and 10 from MD. One mental health center in each state will work with the study, with these mental health centers already having established relationships with the middle schools, with clinicians placed in these schools .7 FTE or 3.5 days per week. In MD, the site will be [REDACTED] (urban), with one school district and all 10 middle schools coming from this

PRINCIPAL INVESTIGATOR: [name]

site. In SC, the site will be [REDACTED] County (suburban and rural). Letters of support from mental health center leaders and the two school districts are included, reflecting the strong partnerships already established between the mental health centers and these districts.

Utilizing the demographic information available from each site's state Department of Education database, participating schools are predominately male (52%) and White (45%), followed by Black/African American (37%), Asian and Multiracial (3%), and less than one percent American Indian and Pacific Islander, with 12% identifying as Hispanic. Current prevalence estimates (2,14) predict that 20% of youth will meet criteria for a more serious EB problem. Due to random school assignment to condition, we predict these percentages will be evenly split across Wellness and Partnership.

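### The School Climate Survey is specified as an end-of-year measure, but three of its five listed waves are in the fall; the first is at or near launch with no stated role, and a trend over years is confounded with season

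*Combined protocol and SAP*

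**What the plan says.** Under Study Design, Measures and Measurement Plan, students and staff complete the School Climate Survey "once annually at the end of each academic year for the four years of intervention vs. comparison", with 2019-20 to 2022-23 named as those four years. The same section reports that, because of COVID-19, "the team was unable to collect SCS data from students in" one site in 2019-20. The site's name is redacted, but South Carolina's data are described as intact. For the affected site the plan says "we will still be able to document trends in time in school climate in" that site over years 2-4.

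The Analytic Plan gives different dates for the same survey: "collected fall, 2019; fall, 2020; fall, 2021; spring, 2022; and spring, 2023". It offers these data "to explore the impact of the Partnership intervention on this variable", without separating a baseline wave from outcome waves.

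On exposure, Study Population and Setting says "Intervention will begin during the 2019-20 school year", and section D, Study Design/Approach, says "Year 1 will involve administrative start up, collection of pre-assessments and intervention launch". The climate survey is not named among those pre-assessments. A pre-study year (2018-19) is specified for academic records but not for climate.

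**The concern.** The two schedules give the data different meanings. An end-of-year wave follows that year's intervention. A fall wave comes before most of that year's delivery and includes sixth graders who have just arrived. On the listed dates, the 2019-20 wave falls around launch, although the measurement plan counts 2019-20 as the first year of intervention versus comparison. A reader cannot tell whether fall 2019 is a baseline or an outcome.

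The change from fall to spring collection also comes partway through the series. If climate ratings differ between the start and the end of a school year for any reason, that difference lines up with calendar time and can be read as change over years. A supportive school culture is part of the hypothesized mechanism, so how the climate results are read matters to the interpretation of the trial, even though climate is not a primary outcome.

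**Working it through.** **The two schedules by school year**

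| School year | Measures and Measurement Plan | Analytic Plan |
|---|---|---|
| 2019-20 | spring 2020 | fall 2019 |
| 2020-21 | spring 2021 | fall 2020 |
| 2021-22 | spring 2022 | fall 2021 and spring 2022 |
| 2022-23 | spring 2023 | spring 2023 |

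Four waves are specified and five are listed. Only spring 2022 and spring 2023 appear in both columns, so three of the five listed waves contradict the specification.

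**Season and time at the affected site.** On the listed dates, years 2-4 are fall 2020, fall 2021, spring 2022 and spring 2023. The documents give no months, so October and April are assumed here.

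- Time in months from October 2020: 0, 12, 18, 30 (mean 15; deviations -15, -3, 3, 15).
- Season (0 fall, 1 spring): 0, 0, 1, 1.
- Sum of squares for time: 225 + 9 + 9 + 225 = 468. Sum of squares for season: 1. Cross-product: 3 + 15 = 18.
- Correlation: 18/√468 = .83.
- If nothing changes except a fall-to-spring shift of s, the fitted linear slope is 18/468 = 0.0385 s per month, or 0.46 s per year. Over the 30 months this is 30 × 0.0385 s = 1.15 s, so the whole seasonal shift appears as trend.
- Varying the assumed months (fall at 0.70 to 0.80 of the calendar year, spring at 0.25 to 0.40) gives correlations of .82 to .86 and slopes of 0.44 to 0.47 s per year.

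**All five waves.** Adding October 2019 (month -12) gives a time sum of squares of 1051.2, a season sum of squares of 1.2 and a cross-product of 28.8. The correlation is 28.8/√(1051.2 × 1.2) = .81, and the slope is 28.8/1051.2 = 0.0274 s per month, or 0.33 s per year. Over the same range of months these are .80 to .84 and 0.32 to 0.33 s.

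**Can season be separated?** Yes, at a cost in precision. With a season term in the four-wave series, the slope comes only from the two same-season one-year differences. The usable sum of squares for time falls from 468 to 4 × 6² = 144, so the slope's variance rises by a factor of 468/144 = 3.25 for a given residual variance.

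**The arm contrast.** A season shift common to both arms adds the same amount to each arm at each wave, so it cancels from the same-wave difference. Fitting arm, time and arm-by-time to five waves with a common shift gave an arm-by-time coefficient of zero. When the shift was made to differ between arms by 0.2 units, the coefficient was 0.065 units per year (0.325 × 0.2).

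**The case against.** The best defence is that no climate model is written down, so no misuse of the data is documented. That is correct, and it rules out three stronger readings.

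- A reader might infer that fall 2019 is pooled as an outcome and dilutes the arm effect, since one of five equally weighted waves would carry no effect (20%). Equal pooling is not stated anywhere. Counting completed school years of exposure, the listed waves are 0, 1, 2, 3 and 4. Without fall 2019 the mean is (1 + 2 + 3 + 4)/4 = 2.5 years, the same as for four end-of-year waves. What can be said is that the role of fall 2019 is unstated.
- A reader might infer that the COVID-19 explanation is wrong, because the Recruitment Plan dates school closures from March 2020, after any fall 2019 wave. The listed dates are not broken down by site. South Carolina may have been surveyed in fall 2019 with the other site planned for spring 2020, in which case the explanation is coherent. This shows that dates by site are needed, but not that there is a further error.
- A reader might infer that a seasonal change will be reported as a trend. The plan speaks of trends without naming a linear slope, and it gives no evidence that s differs from zero.

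It is also fair to say that climate is outside the primary aims. Aim 1 covers services and satisfaction, Aim 2a lists grades, attendance, lateness and discipline, and the Analytic Plan proposes only to explore climate.

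The defence does not remove the contradiction between the two schedules, the unstated role of the near-launch wave, or the alignment of season with time on the listed dates.

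**Conclusion.** The concern holds as a contradiction with a limited consequence. Three of the five listed waves do not fit the stated schedule, 2021-22 has two waves, and the wave at or near launch is not identified as a baseline. If the Analytic Plan's dates are the true record, a within-site or within-arm trend over years 2-4 is strongly but not completely confounded with season: correlation about .82 to .86, and 0.44 to 0.47 s per year of false slope under a linear fit. These figures rest on assumed survey months, and the size and sign of s are unknown.

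The randomized contrast at the same wave is not biased by season, provided both arms were surveyed together and season acts equally in them. No primary estimate, error rate or sample size is affected. The change is still worth making, because it improves the exploratory climate analysis using data already listed.

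**What to change.** 1. Reconcile the Measures and Measurement Plan with the Analytic Plan, and state the date of each climate wave by site and by respondent type.
2. Use fall 2019 as a baseline, not as an outcome wave. Enter it as a school-mean covariate from the same respondent type, where it was collected, after checking the survey date against launch at each school.
3. For schools without it, use a missing-baseline indicator or report an unadjusted sensitivity analysis. These schools include the two added in Year 3. Do not substitute staff means for student means: students and staff complete different surveys, and the substitution would follow site.
4. Fit wave as categorical, with arm-by-wave contrasts over the post-launch waves.
5. Limit statements about trends over years to same-season waves, or include a season term.

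The cost is revised wording in two sections and recoding of wave in the climate model. The drawbacks are that baseline will be unavailable for some schools, possibly for all student data at one site, and that same-season trends use fewer waves and are less precise.
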